7.2.3. Clinical Laboratory Evaluation

Blood and urine samples will be collected at each specified study visit (see [Table 1](#), Schedule of Activities). Unscheduled clinical labs may be obtained at any time during the study to assess any perceived safety concerns or in accordance with the guidelines for subject safety monitoring and discontinuation. Clinically significant abnormal findings should be recorded as AEs per [Section 8.5](#).

The following laboratory tests will be performed locally during the study at the VOC/Treatment-Ready Screening visit, End of Treatment, and the Day 35 Post-Discharge Follow-Up visit:

Table 3. Clinical Laboratory Evaluations – Local Laboratory	
Hematology	
Hemoglobin	Reticulocyte count
Hematocrit	Platelet count
Red blood cell (RBC) count	WBC count with differential
Serum Chemistry	
Blood urea nitrogen (BUN)	Alanine aminotransferase (ALT/SGPT)
Creatinine	Aspartate aminotransferase (AST/SGOT)
Electrolytes (Sodium, Potassium, Chloride and Bicarbonate) with glucose	Fractionated bilirubin
Lactate dehydrogenase (LDH)	
Urinalysis	
Protein	Blood
Glucose	Nitrite
Ketones	Leukocyte esterase
Estimated Glomerular Filtration Rate (eGFR) at VOC/Treatment-Ready Screening visit (calculated using age appropriate formula in Appendix 1)	

Note: A hemoglobin electrophoresis sample will be collected at the VOC/Treatment-Ready Screening visit and analyzed at the central laboratory only if the subject's diagnosis (ie, laboratory result by hemoglobin electrophoresis, HPLC, or genotype analysis) cannot be source documented.

7.2.4. Triggered Requirements

This section presents specific safety parameters of concern for the study drug that require follow-up action.

Table 4. Triggered Requirements

Condition	Action
Changes in Renal Function	
If the repeat eGFR result is $\leq 60 \text{ mL/min}/1.73 \text{ m}^2$	Stop study drug administration
Severe Acute Chest Syndrome (Section 7.2.4.2.1)	Stop study drug administration
Severe Cutaneous Manifestations (Section 7.2.4.3.1)	Stop study drug administration

7.2.4.1. Changes in Renal Function

The identification of deteriorating renal function could be based on rising serum creatinine or blood urea nitrogen (BUN), worsening proteinuria, or other abnormalities on urinalysis (with or without microscopic evaluation), or a change in clinical features (such as changes in urine output or physical findings such as pedal edema). Based on the clinical judgment of the investigator if any of these or other clinical features develop, the eGFR is to be repeated (refer to [Appendix 1](#) for calculation). Given that subjects are eligible to participate in this study if their eGFR is >60 mL/min/1.73 m², if the repeat eGFR is ≤ 60 mL/min/1.73 m² treatment is to be stopped.

7.2.4.2. Acute Chest Syndrome Events

For the purposes of this protocol, ACS will be defined by NIH treatment guidelines^{[24,25](#)} as follows:

- New pulmonary infiltrate involving at least one complete lung segment consistent with the presence of alveolar consolidation, (excluding atelectasis) AND one or more of the following:
 - a. Chest pain;
 - b. Temperature $>38.5^{\circ}$ C;
 - c. Tachypnea;
 - d. Wheezing or rales;
 - e. Cough.

Note: the clinical signs and symptoms of ACS were updated in the NIH Evidence-Based Management of Sickle cell Disease: Expert Panel Report (2014), however, for the purposes of this protocol the above definition will continue to be used^{[29](#)}

Subjects will be monitored for development of ACS throughout the study. The identification of ACS will be made by the study site staff and communicated to Pfizer or designee. Clinical events that might represent ACS may be identified by the Pfizer Study Team or designee during the review of subject data listings or by site monitors during routine monitoring of subject study records. The Pfizer study team will notify the study site staff if they identify a potential ACS event that has not been reported by the site. All reported cases of potential ACS that occur from the time of the subject's first dose of study drug through the subject's last visit will be evaluated by the Acute Chest Syndrome Safety Endpoint Adjudication Committee (ACS-SEAC; see [Section 9.7.1](#)).

The Pfizer Study Team or designee will provide a listing of specific documents needed to support ACS event adjudication by the ACS-SEAC. Obtaining the documentation will be the responsibility of the study site staff. ACS event documentation will include, but is not limited to any of the following: daily hospital/clinic notes and physical examination documentation, hospital discharge summaries, operative and procedural reports, chest x-rays,

vital signs including oximetry, laboratory reports and results of other diagnostic tests, autopsy reports and death certificate information.

7.2.4.2.1. Severe ACS (Withdraw from Study Drug Administration)

For the purposes of this protocol, severe acute chest syndrome is defined as an ACS diagnosis as above ([Section 7.2.4.2](#)), and the requirement for at least one of the following:

- ICU Transfer;
- Mechanical ventilation;
- Oxygen requirement of >50% FiO₂, or the use of high flow oxygen delivery system, or bilevel positive airway pressure (BiPAP) or continuous positive airway pressure (CPAP).

Subjects that develop severe ACS are to be terminated from study drug administration. Subjects that develop mild or moderate cases of ACS may continue to receive treatment with study drug.

7.2.4.3. Cutaneous Manifestations

The identification of cutaneous manifestations and acute skin rashes will be made by the study site staff and communicated to Pfizer or designee. Clinical events of cutaneous manifestations and/or acute skin rashes may also be identified by the Pfizer Study Team or designee during the review of subject data listings or by site monitors during routine monitoring of subject study records. The Pfizer study team will notify the study site staff if they identify a potential event that has not been reported by the study site staff. All cases of cutaneous manifestations and acute skin rashes that develop from the time of the subject's first dose of study drug through the subject's last visit will be independently evaluated by the Cutaneous Manifestations Safety Endpoint Adjudication Committee (CM-SEAC; see [Section 9.7.2](#)) to determine if they constitute severe and/or generalized cutaneous events.

A dermatologic evaluation of severe and/or generalized acute skin rashes should be undertaken locally. Evaluation of less severe cases should also be undertaken where feasible. A biopsy should be considered based upon this dermatologic evaluation. For severe and/or generalized cutaneous reactions and any reactions that are considered "unexpected" or unusual, photographs should be obtained per instructions provided in a separate study manual and differential blood count and serum aminotransferase assays performed. Photographs and blood samples are strongly encouraged at the time of the event in cases of mild or transient cutaneous manifestations (eg, mild and transient allergic reactions or exacerbation of pre-existing conditions such as eczema).

The Pfizer Study Team or designee will provide a list of specific documents needed to support rash adjudication by the CM-SEAC. Obtaining the documentation will be the responsibility of the study site staff. Rash event documentation will include, but is not limited to any of the following: photographs, hospital discharge summaries including dermatologic evaluation at the time of rash, operative reports, pathology reports of biopsy (if

done), laboratory reports (including differential blood count and serum aminotransferase), clinic notes, results of other diagnostic tests, autopsy reports and death certificate information.

7.2.4.3.1. Severe Cutaneous Manifestation (Withdraw from Study Drug Administration)

For the purposes of this protocol, a severe cutaneous manifestation that would require study drug discontinuation is defined as the occurrence of any of the following:

- Any skin eruption with mucosal or visceral involvement.
- Any skin eruption that includes blisters, vesicles, pustules or purpura.
- Any skin eruption that involves >50% of the body surface area.

Decisions around withdrawal from study drug administration for cutaneous manifestations not meeting the above criteria will be made on a case-by-case basis by the investigator who, if appropriate, may discuss the case with a local dermatologist, and/or the Sponsor's Medical Monitor, and/or members of the CM-SEAC.

7.3. Pregnancy Testing

For female subjects of childbearing potential, a serum or urine pregnancy test, with sensitivity of at least 25 mIU/mL, will be performed at the VOC/Treatment-Ready Screening visit prior to study drug administration, at the End of Treatment visit, and at the Day 35 Post-Discharge Follow-Up visit. A negative pregnancy test result is required before the subject may receive the study drug. Study drug should not be administered if the pregnancy test is indeterminate or positive. Pregnancy tests will also be done whenever one menstrual cycle is missed during the active treatment period (or when potential pregnancy is otherwise suspected), and at the end of the study to confirm the subject has not become pregnant during the study. In the case of a confirmed pregnancy, the subject will be withdrawn from study drug but may remain in the study. Pregnancy tests may also be repeated as per request of IRB/ECs or if required by local regulations.

090177e1915da01b\Approved\Approved On: 16-Jul-2019 18:44 (GMT)

090177e1915da01b\Approved\Approved On: 16-Jul-2019 18:44 (GMT)

For more information, contact the Office of the Vice President for Research and Economic Development at [contact] or [contact].

11. **What is the primary purpose of the *Journal of Clinical Endocrinology and Metabolism*?**

[REDACTED]

[REDACTED]

[REDACTED]

7.6. Stored Specimens

Any remaining plasma and serum

will be stored for exploratory retrospective analyses associated with trial and program related endpoints (eg, safety, efficacy), the subjects' disease, the drug's mechanism of action, or to support personalized medicine approaches. Retaining the residual plasma and serum specimens for analysis at a

later date makes it possible to better understand the drug's mechanism of action and to seek explanations for differences in, for example, exposure, efficacy, tolerability, or safety not anticipated prior to the beginning of the study.

To protect subjects' confidentiality, the stored specimens and data generated from them will be coded with the subject's study ID number. Samples will be kept in a facility accessible only by badge-swipe. Data will be stored on password-protected computer systems. The key between the code and the subject's personal identifiers will be held at the study site; the researchers using the specimens and data generated from them will not have access to the key nor any personally identifying information. Specimens will only be used for the purposes described here and in the informed consent document/patient information sheet; any other uses require additional ethical approval. Unless a time limitation is required by local regulations or ethical requirements, specimens will be stored indefinitely to allow for future research on the topics described here, including research conducted during the lengthy drug development process and also post-marketing research. Subjects can withdraw their consent for the use of their specimens at any time by making a request to the investigator, in which event any remaining specimen will be destroyed; data already generated from the specimens will continue to be stored to protect the integrity of existing analyses. It is very unlikely that results generated from the specimens will have any clinical, diagnostic, or therapeutic implications for the individual study participants. Subjects are notified in the informed consent document/patient information sheet that their results will not be given to them, unless required by local laws or regulations, in which case results will be returned via the investigator. Results will not be provided to family members or other physicians; nor will they be recorded in the subject's medical record. There is no intention to contact subjects after completion of the clinical trial.

It is possible that the use of these specimens may result in commercially viable products. Subjects will be advised in the informed consent document/patient information sheet that they will not be compensated in this event.

7.7. Total Blood Volume

Table 7. Total Blood Volume in Adults (≥ 18 year of age)

Study Participation	Blood Volume (mL)								
Study Visit/Contact ID	Screen/Pre-Loading Dose	First 24 hours/ Post Loading Dose	Pre Dose 2 or 3	Post Dose 2 or 3	Pre Dose 5 or 6	End of Treatment	Day 35 Post-Discharge Follow-Up visit	Total	
Clinical Laboratories	9ml					9ml	9ml	27ml	
Hemoglobin Electrophoresis ^a	4ml							4ml	
Pregnancy Test ^b	2ml					2ml	2ml	6ml	
Total									

a. Sample will only be collected if subject does not have a documented diagnosis of SCD.

b. Pregnancy test can be either serum or urine as long as the sensitivity is at least 25 mIU/mL. Sample will only be collected from female subjects of childbearing potential.

Table 8. Total Blood Volume in Pediatrics 12-17 years of age

Study Participation	Blood Volume (mL)								
Study Visit/Contact ID	Screen/Pre-Loading Dose	First 24 hours/ Post Loading dose	Pre Dose 2 or 3	Post Dose 2 or 3	Pre Dose 5 or 6	End of Treatment	Day 35 Post-Discharge Follow-Up visit	Total	
Clinical Laboratories	4.5ml					4.5ml	4.5ml	13.5ml	
Hemoglobin Electrophoresis ^a	4ml							4ml	
Pregnancy Test ^b	2ml					2ml	2ml	6ml	
Total									

a. Sample will only be collected if subject does not have a documented diagnosis of SCD.

b. Pregnancy test can be either serum or urine as long as the sensitivity is at least 25 mIU/mL. Sample will only be collected from female subjects of childbearing potential.

Table 9. Total Blood Volume in Pediatrics 6-11 years of age

Study Participation	Blood Volume (mL)								Total
	Study Visit/Contact ID	Screen/Pre-Loading Dose	First 24 hours/ Post Loading Dose	Pre Dose 2 or 3	Post Dose 2 or 3	Pre Dose 5 or 6	End of Treatment	Day 35 Post-Discharge Follow-Up visit	
Clinical Laboratories	4.5ml						4.5ml	4.5ml	13.5ml
Hemoglobin Electrophoresis ^a	4ml								4ml
Pregnancy Test ^b	2ml						2ml	2ml	6ml
Total									

a. Sample will only be collected if subject does not have a documented diagnosis of SCD.

b. Pregnancy test can be either serum or urine as long as the sensitivity is at least 25 mIU/mL. Sample will only be collected from female subjects of childbearing potential.

8. ADVERSE EVENT REPORTING

8.1. Adverse Events

All observed or volunteered AEs regardless of treatment group or suspected causal relationship to the study drug will be reported as described in the following sections.

For all AEs, the investigator must pursue and obtain information adequate both to determine the outcome of the AE and to assess whether it meets the criteria for classification as a

serious adverse event (SAE) requiring immediate notification to Pfizer or its designated representative. For all AEs, sufficient information should be obtained by the investigator to determine the causality of the AE. The investigator is required to assess causality.

Follow-up by the investigator may be required until the event or its sequelae resolve or stabilize at a level acceptable to the investigator, and Pfizer concurs with that assessment.

As part of ongoing safety reviews conducted by the Sponsor, any non-serious adverse event that is determined by the Sponsor to be serious will be reported by the Sponsor as an SAE. To assist in the determination of case seriousness further information may be requested from the investigator to provide clarity and understanding of the event in the context of the clinical study.

8.2. Reporting Period

For SAEs, the active reporting period to Pfizer or its designated representative begins from the time that the subject or subject's parent(s)/legal guardian/legally acceptable representative provides informed consent/assent (either Pre-VOC/Study Entry consent or VOC/Treatment-Ready consent depending on the subject's entry point into the study), which is obtained prior to the subject's participation in the study, ie, prior to undergoing any study-related procedure and/or receiving study drug, through and including the subject's last visit or 28 calendar days after the last administration of the study drug, whichever is longer. Serious adverse events occurring to a subject after the active reporting period has ended should be reported to the Sponsor if the investigator becomes aware of them; at a minimum, all serious adverse events that the investigator believes have at least a reasonable possibility of being related to study drug are to be reported to the Sponsor.

AEs (serious and non-serious) should be recorded on the CRF from the time the subject has taken at least one dose of study drug through the subject's last visit.

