3.3. Approximate Duration of Subject Participation

Subjects who enter the study in crisis will participate in the study for approximately 44 days. This includes 1 day for screening, up to 8 days for the double-blind treatment period, and a post-discharge follow-up period of approximately 35 days. Under certain situations,

complications may occur during the subject's hospitalization and the subject's participation in the study may exceed 44 days.

Subjects who enter the Pre-VOC period of the study while well (ie, not in VOC) will participate in the study for more than 44 days. The duration of the pre-VOC period for these subjects is variable and unpredictable. Once the subject has a VOC requiring hospitalization, affirms informed consent and meets all eligibility criteria, their participation in the double-blind treatment period and follow-up period of the study will be approximately 44 days, as described above.

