6.4.3. Visit 4, Day 35 Post-Discharge Follow-Up/Early Termination

The following activities are to be performed 35 (± 5) days after discharge. However, if the subject is experiencing a VOC or other acute SCD-related event, the visit should be delayed until the acute event has resolved. If the subject terminates from the study early, these same procedures are to be performed no sooner than 28 days from the last dose of study drug.

1. Conduct a targeted physical exam assessing the following at a minimum: skin, chest, respiratory, cardiovascular, abdominal and musculoskeletal systems. Particular attention will be directed at areas affected by pain. Additional body systems may be examined at the discretion of the investigator.
2. Record adverse events.
3. Record concomitant medications.
4. Record concomitant non-drug treatments/procedures.
5. Collect vital signs (temperature [$^{\circ}$ Celsius], respiratory rate, pulse, blood pressure, and pulse oximetry).
6. Collect blood samples for:
 - Hematology panel (see [Table 3](#)); local laboratory,
 - Serum Chemistry (see [Table 3](#)); local laboratory,

7. Collect urine for Urinalysis; to be analyzed at the local laboratory.
8. Perform contraception check, if applicable (see [Section 4.3.1](#)). Document discussion with subject.
9. Perform pregnancy test on female subjects of childbearing potential.

[REDACTED]

11. Obtain informed consent/assent from the subject for participation in the open-label extension study, Study B5201003, as appropriate. Informed consent/assent for Study B5201003 may be obtained from the time of the Day 35 Post-Discharge Follow Up visit up to 180 days after the Day 35 Post-Discharge Follow-Up visit.

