8.5. Analysis of Safety Data

For Cohort 1 and Cohort 2 combined, Cohort 1 by age group and Cohort 2 alone based on the Safety Analysis Set, the safety data (eg, AEs, SAEs, vital signs, physical examinations, laboratory tests) will be summarized in accordance with CDISC and Pfizer Standards (CaPS). In addition, for Cohort 1 and Cohort 2 combined ONLY, a 3-tier approach described below will be used for summarizing AE data. Safety data that will be specifically summarized include:

- Adverse events:

[figure not shown]
The analyses of adverse events will make use of the 3-tiered approach described below for Cohort 1 and Cohort 2 combined ONLY. These analyses will be considered exploratory. Under the 3-tier approach, AEs are classified into one of three tiers with different analyses performed for different tiers.

- Tier-1 events: These are events that are pre-specified events of clinical importance and are maintained in the custom AE term list system (CAETeLiSt).
- Tier-2 events: These are events that are not tier-1 but are “common”. A MedDRA Preferred Term (PT) is defined as a Tier-2 event (“common” event) if there are at least 4 in any treatment group.
- Tier-3 events: These are events that are neither tier-1 nor tier-2 events. Tier-3 events will be reported with observed proportions by treatment group without comparative statistics.

For Tier-1 events, the unconditional exact method for 95% CI for risk difference and p-value proposed by Chan and Zhang (1999) will be used to compare rivipansel with placebo. For Tier-2 events, the normal approximation will be used for calculating the 95% CI for risk difference. There will be no adjustment for multiple comparisons or stratification factors in the analyses.

- Safety laboratory tests reported according to CDISC and Pfizer standards (CaPS). Shift tables summarizing the changes in laboratory test results from baseline will be presented (see Appendix [Section 10.3](#) for details on shift tables).
- Incidence of clinically significant changes in physical examination will be summarized using descriptive statistics.
- Change from baseline at End of Treatment and at the Day 35 Post-discharge Visit in vital signs (eg, blood pressure, heart rate, temperature, respiratory rate, and pulse oximetry) will be reported using descriptive statistics.
- Incidence of adjudicated AEs will be analyzed using the same approach as for Tier-1 events.

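### Adverse events are counted to a visit timed from discharge, so a shorter stay on rivipansel gives the placebo arm slightly longer observation and a small bias in the crude safety comparison

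*Protocol*

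**What the plan says.** Collection window. Protocol section 8.2 (Reporting Period) says that "AEs (serious and non-serious) should be recorded on the CRF from the time the subject has taken at least one dose of study drug", and recording continues to the last visit. Active reporting of serious events ends at the "last visit or 28 calendar days after the last administration of the study drug, whichever is longer". ACS and cutaneous events are adjudicated over the same span, from first dose to last visit (Protocol sections 3.1, 7.2.4.2 and 7.2.4.3).

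Where the window ends. Protocol section 3.3 describes "a post-discharge follow-up period of approximately 35 days". The Schedule of Activities times Visit 4 at 35 (±5) days from discharge, not from first dose. Protocol section 6.4.3 adds that "if the subject is experiencing a VOC or other acute SCD-related event, the visit should be delayed until the acute event has resolved".

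Analysis. SAP section 8.5 gives Tier-1 events an exact confidence interval and p-value for the risk difference. Tier-2 events get a normal-approximation interval for the risk difference, and Tier-3 events get observed proportions only. For ACS and cutaneous events, "Incidence of adjudicated AEs will be analyzed using the same approach as for Tier-1 events". The section labels the tiered analyses exploratory. The visible text has no common window from first dose, no person-time rate and no time-to-first-event analysis for adverse events. VOC re-hospitalization is treated differently: its windows are fixed at 3, 7, 14 and 30 days and start at discharge.

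**The concern.** The primary and first key secondary endpoints are times to readiness-for-discharge and to discharge, so the trial is built to show that rivipansel shortens the stay. The safety window is that stay plus a roughly constant follow-up. If the drug works, its subjects are watched for fewer days. Even with identical daily event rates, a smaller share of them will then have at least one recorded event.

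A crude risk difference cannot separate this from better safety. The direction is known in advance and favours rivipansel. Safety is the trial's secondary objective, and adjudicated ACS and cutaneous events are named safety endpoints that receive a confidence interval and p-value. At stake is a slight understatement of any true excess on rivipansel.

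**Working it through.** **1. The plan's own figure.** Protocol section 9.1 assumes exponential times with medians of 156 h (placebo) and 106 h (rivipansel), two-sided alpha 0.05 and 90% power. The hazard ratio is 106/156 = 0.679 and its log is -0.3864, as in SAP section 10.4. Schoenfeld's formula, 4 × (1.960 + 1.282)² / 0.3864², gives 282 events, matching the stated 282. The planning inputs are therefore read correctly.

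**2. Length of observation.** Window = stay in days + 35. Stay is represented in three ways:
- the planning medians for readiness-for-discharge;
- the exponential means they imply (156/ln 2 = 225.06 h; 106/ln 2 = 152.93 h);
- the Phase 2 mean times to VOC resolution (148 and 110 h, Protocol section 1.2.3).

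| Input | Placebo window | Rivipansel window | Extra on placebo | Ratio |
|---|---|---|---|---|
| Planning medians | 6.50 + 35 = 41.5 d | 4.42 + 35 = 39.4 d | 2.1 d | 1.053 |
| Exponential means | 9.38 + 35 = 44.4 d | 6.37 + 35 = 41.4 d | 3.0 d | 1.073 |
| Phase 2 means | 6.17 + 35 = 41.2 d | 4.58 + 35 = 39.6 d | 1.6 d | 1.040 |

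These inputs only stand in for actual stay. As a check, Protocol section 1.2.5 gives Phase 2 differences in median time to discharge of 56 h and 55 h at the two doses, about 2.3 days. That lies inside the 1.6 to 3.0 day range.

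**3. Effect on crude proportions.** Assume the same constant event rate in both arms. If the incidence on rivipansel is p and the window ratio is r, the expected placebo incidence is 1 - (1 - p)^r.

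- r = 1.073: 20% becomes 21.3% and 30% becomes 31.8%, spurious differences of 1.3 and 1.8 points.
- r = 1.040: 20% becomes 20.7% and 30% becomes 31.0%, differences of 0.7 and 1.0 points.
- Rare events at r = 1.073: incidences of 1%, 2% and 5% give 0.07, 0.14 and 0.35 points.

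Letting stays vary exponentially between subjects, a 30% placebo incidence corresponds to 28.4% on rivipansel, a difference of 1.6 points. Among the incidences tried this way (2% to 70%), the largest difference is 2.2 points, at 50%.

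**4. Against the precision available.** With 300 subjects randomized 1:1, take 150 per arm. The 95% half-width for the risk difference is about 9.2 points for 20% against 21.3%, and about 10.5 points for 30% against 31.8%. The bias is a fraction of either.

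**5. Whether a fixed 30-day window is available.** Visit 4 is no earlier than 35 - 5 = 30 days after discharge, so every completer is observed for at least 30 days from first infusion. Both arms then have equal windows, and the expected difference under equal constant rates is zero.

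**6. What that window does not equalise.** It still holds more hospital days on placebo. Suppose the in-hospital rate is k times the later rate (an assumption; the documents give no such figure). At the planning medians the effective exposure ratios are:
- k = 3: planned window (3×6.5 + 35)/(3×4.42 + 35) = 1.13; 30-day window (3×6.5 + 23.5)/(3×4.42 + 25.58) = 1.11.
- k = 10: 1.26 and 1.27.

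The fixed window removes the part due to unequal observation time. It does not remove a part due to events being more frequent, or more closely looked for, in hospital.

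**The case against.** The strongest case against acting is size. On every stay input the bias is far inside the confidence interval. For the rare skin events that matter most (Phase 2 had one serious AGEP among 76 subjects) it is well under half a point. This stands, and it sets the severity. So does the SAP's exploratory label, although a label does not remove a bias from an estimate.

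The 3.0-day figure is the upper end. Exponential stays at the planning medians put 57% (placebo) and 72% (rivipansel) out within 8 days, whereas SAP section 10.1.3 reports that 79% of Phase 2 subjects were discharged by then. The assumed tail is probably too long, so the result is given as a range.

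Three stronger readings are tempting but not supported:
- A reader might infer that postponing Visit 4 for acute events adds to the bias against placebo. The rule applies to both arms. It would lengthen the rivipansel window if that arm had more late crises, and it starts only once the event is under way. It has no fixed direction.
- A reader might infer that any deficit of ACS on rivipansel would be an artefact. The protocol treats ACS as a complication of the crisis, so fewer cases after a shorter crisis could be real benefit.
- A reader might infer that the 30-day analysis should replace the planned one. That would remove late events from every between-arm comparison and could hide a late excess.

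The analysis window may also differ from the collection window. SAP 8.5 reports treatment-emergent events under sponsor standards that are not in the documents, and SAP 10.2 is largely redacted. A cut-off counted from last dose would not clearly equalise the arms, because dosing stops when criterion 1 is met. It could change the size.

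**Conclusion.** The mechanism is in the text and its direction is predictable. If rivipansel shortens the stay as planned, placebo is observed about 4 to 7% longer. Crude risk differences are then tilted towards rivipansel by roughly 0.7 to 1.8 points for events with 20 to 30% incidence, and by under 0.4 points at 5% or less.

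This rests on three assumptions: an equal and constant event rate in both arms, readiness or resolution time standing in for stay, and an analysis window equal to the recording window. With no difference in stay there is no bias. The VOC re-hospitalization endpoints are unaffected because their windows start at discharge.

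A reader might infer that the safety comparison is unsound or that a material harm would be concealed. The figures do not support that; alone, the effect would rarely change a conclusion. Severity is minor, and the change is a cheap improvement.

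**What to change.** In SAP section 8.5, keep the planned comparisons through the last visit and add two items:

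1. For Tier-1, Tier-2 and adjudicated ACS and cutaneous events, repeat the same risk-difference analysis restricted to events with onset within 30 days after the start of the first infusion.
2. Tabulate these events separately for the in-hospital and post-discharge periods, because assessment is daily in hospital and limited afterwards to two scheduled contacts and one visit.

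The cost is SAP wording, a filter on onset date and a few extra tables, with no new data. The 30-day analysis omits later events, but these remain in the through-last-visit comparison. It equalises observation time only; the split table is there to show any remaining difference in ascertainment. SAP section 1 records that the study team was still blinded at that amendment, so the rule could be set before unblinding.
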